**Study Objective(s)**

**Part 1:**

**Primary**

**To compare the relationship between BMI-Z score and cardiometabolic risk factors in youth with DS, and in age-, sex-, race-, ethnicity-, and BMI-Z score-matched controls.**

- a) Compare cardiometabolic risk factors [non-HDL cholesterol, lipoprotein subclass particles, blood pressure, insulin resistance (measured by HOMA-IR), insulin sensitivity index (ISI), glucose tolerance, inflammatory markers, and adipokines)] in adolescents with DS and in matched controls.
- b) Determine the extent to which adiposity (fat mass by DXA) explains this relationship in DS vs. controls.
- c) Assess cardiac end organ injury (pulse wave velocity (PWV) and left ventricular mass) in relationship to BMI-Z score in adolescents with DS and controls. Determine whether BMI-Z or other measures of adiposity (skin-fold thickness, waist circumference) better discriminates adolescents with DS at increased cardiometabolic risk.

**Hypothesis:** DS is associated with worse cardiometabolic risk factors for a given BMI-Z compared to controls. This difference arises at least in part, from increased adiposity.

---

---

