### **2.1 Primary Aim 1**

The primary objective is to compare the relationship between BMI-Z score and cardiometabolic risk factors in youth with DS, and in age-, sex-, race-, ethnicity- and BMI-Z score- matched controls.

a) Compare cardiometabolic risk factors [non-HDL cholesterol, lipoprotein subclass particles, blood pressure, insulin resistance (measured by HOMA-IR), insulin sensitivity index (ISI), glucose tolerance, inflammatory markers, and adipokines)] in adolescents with DS and in matched controls.

b) Determine the extent to which adiposity (fat mass by DXA) explains this relationship in DS vs. controls.

---

c) Assess cardiac end organ injury (pulse wave velocity (PWV) and left ventricular mass) in relationship to BMI-Z score in adolescents with DS and controls. Determine whether BMI-Z or other measures of adiposity (skin-fold thickness, waist circumference) better discriminates adolescents with DS at increased cardiometabolic risk.

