#### **5.1.7 Left Ventricular (LV) Mass**

LV mass will be measured by echocardiography, as described by the American Society of Echocardiography's guidelines. Per these guidelines the equation of Devereux et al will be used. LV Mass Index (LV mass/height2.7), has been used to normalize LV mass to body size. However, this index increases with decreasing height, which is not ideal for children with DS. Use of centile curves and z-scores is another strategy to account for

---

lean mass (LM), which may also be different in children with DS. We will measure LM by DXA and can thus normalize LV mass directly.

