Primary Aim: The primary aim is to compare the relationship between BMI-Z and cardiometabolic risk factors in youth with DS and matched controls. This relationship may be different in children with DS with and without CHD. In order to model the analyses appropriately, the primary outcome variables will be compared between children with DS with and without hemodynamically significant CHD. If the groups differ, subsequent analyses will include a dummy variable indicating presence/absence of hemodynamically significant CHD. Descriptive data analysis will summarize distributions of all risk factor measures (age, weight, BMI-Z, non-HDL-C, lipid levels, lipoprotein subclass particles, BP, HOMA-IR, ISI, inflammatory markers, adipokines, CPP, PWV, LV mass, gender, race, ethnicity, pubertal stage, pre-diabetes and diabetes status, physical activity). Subjects with DS will be compared to age-, sex-, race-, and BMI-Z matched controls, first by comparison of risk factor distributions by DS status. Next, we will fit separate regression models for each risk factor, with DS as the exposure of interest, adjusted for potential confounders, including pubertal stage, family history of CVD, dietary fat intake, and smoking history. Interaction terms among confounders will be used when data frequencies permit. Initial regressions will confirm the size and sign of associations of subject characteristics and CVD risk factors. Complementary analyses will implement propensity scores, using logistic regression to model DS as a function of observed covariates, and then will compare DS and non-DS children for each endpoint using weighted analyses. Weights will be calculated by the inverse of the fitted probability of DS. This method will standardize the comparisons of CVD risk factors by differences in observed characteristics of DS and non- DS children and thus will permit statements such as —If a sample of children otherwise comparable were alternatively DS and non-DS, what would be the differences in CVD risk factors? Finally, we will perform sensitivity analyses as to the potential impact on our results from unobserved potential confounders. Initial analyses will determine whether children with DS differ from their non-DS counterparts in terms of CVD risk factors and will become the basis for addressing the questions in the four sub-aims.

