#### **6.1.1 Aim 1a) BMI-Z scores and DS – CMR factors**

---

To analyze this aim, the statistical model noted above will be modified to include an interaction term between DS and BMI-Z score for each CVD risk factor. An important interaction term will reflect varying association of BMI-Z by disease status. Based on preliminary data we estimate 50% of subjects with DS will have BMI $\geq$ 85%ile and undergo an OGTT. We will compare prevalence of IGT or IFG and T2DM between groups. (Although DS is associated with increased risk for T1DM, this would most likely present acutely and have already been diagnosed if present.)

**6.1.2 Aim 1b) DXA-measured FM** This sub aim will make use of the model in Aim 1a. Inclusion of FM in explaining CMR factors in the model should offset any statistical interaction between BMI-Z and DS status.

**Aim 1c) PWV [and LV Mass]** Using the model outlined previously, we will add PWV as an indicator of end organ damage to assess additional information provided by PWV, especially with regard to the interaction of BMI-Z and CVD risk factor levels. This approach will be used for CPP and LV mass as well.

**6.1.3 Aim 1d) Discrimination ability of BMI-Z and other screening measures** This analysis will be confined to children with DS, and will require for each CVD risk factor the determination before analysis of a threshold of high versus low, in order to evaluate discrimination. With BMI-Z, and each risk factor taken individually, we shall estimate the c-statistic, a measure of discrimination representing the area under the ROC curve of the tradeoff of sensitivity and specificity, for each screening measure as a predictor of high vs. low risk. Finally, we shall compare the additional discriminatory power of adding one screening measure to an existing screening measure, such as WC to BMI-Z to determine whether an additional screen is worth the expense and time. These contrasts will be implemented using the methods outlined by Pepe and colleagues.

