symptoms develop, blood glucose will be checked. In the event of hypoglycemia (blood glucose < 60 mg/dL), the study will be terminated and carbohydrates consumed by the subject. Blood glucose will be monitored until normalization is assured. To minimize subject burden, particularly in this cohort of children with developmental disabilities, we will perform OGTT only in subjects with BMI ≥ 85%. While the aim of the study is to uncover cardiometabolic risk factors in children with DS and to uncover whether adolescents with DS have greater risk for a given BMI z-score, glucose intolerance is unlikely in children with BMI < 85% and the yield of doing OGTT in this subgroup is relatively low. Our team felt that it was crucial to be sensitive to the burden of participation placed on these children with intellectual and developmental disabilities and their families.

Participation in the study involves risks associated with the small amount of radiation exposure associated with the DXA whole body scan for body composition assessment; the total radiation EDE from DXA scans is less than 3 μSv (or 1 mrem). This total amount of radiation is less than the exposure to daily background radiation at sea level (3,000 μSv per year) and is therefore considered minimal risk. Females of childbearing potential undergo a urine pregnancy test prior to the DXA scans. Pregnant females do not have DXA scans performed in order to protect the unborn fetus.

The anthropometric assessment involves measurements of height, weight, circumferences and skinfold thickness. There is a very minor possibility of bruising from the skinfold thickness measurements. The exam will be performed by trained anthropometrists experienced in obtaining measurements in children at all levels of cognitive ability. The measurements are obtained in a private room. The parent is permitted to stay with the child if it increases their comfort with the exam.

The puberty assessment will be performed by pediatric endocrinologists in a private setting. The procedure will be explained to the child in advance, and the parent is permitted to be present if preferred by the child. The exam is performed by highly experienced personnel who are familiar with minimizing distress associated with the exam.

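### Aim 1b names only the BMI-Z by Down syndrome interaction as the result of adding fat mass; the change in the Down syndrome coefficient should be reported as well

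*Combined protocol and SAP*

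**What the plan says.** Section 2.1, item b, sets the objective: "Determine the extent to which adiposity (fat mass by DXA) explains this relationship in DS vs. controls". Section 6.1.2 (Aim 1b) gives the analysis in two sentences. It reuses the Aim 1a model, which contains a DS by BMI-Z interaction for each risk factor, and it states the expected result: "Inclusion of FM in explaining CMR factors in the model should offset any statistical interaction between BMI-Z and DS status". No other Aim 1b result is named.

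The hypothesis in the Protocol Synopsis reads: "DS is associated with worse cardiometabolic risk factors for a given BMI-Z compared to controls". It continues: "This difference arises at least in part, from increased adiposity". Section 8.3.3 repeats the idea, giving as part of the study's aim "to uncover whether adolescents with DS have greater risk for a given BMI z-score".

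The DS coefficient is not absent from the plan. Section 6.1 fits one regression for each outcome "with DS as the exposure of interest, adjusted for potential confounders, including pubertal stage, family history of CVD, dietary fat intake, and smoking history", and says the initial DS versus control analyses "will become the basis for addressing the questions in the four sub-aims". No section says that the DS coefficient will be compared before and after fat mass enters.

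**The concern.** A DS effect on a risk factor can take two forms. The slope on BMI-Z may differ between groups, which is the interaction. Or one group may be worse at the same BMI-Z, which is the DS coefficient. The objective is worded mainly as the first and the hypothesis mainly as the second. Aim 1b names a result only for the first.

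Aim 1b is the mechanistic half of the primary hypothesis. If the extra fat in DS is much the same at every BMI-Z, there is little interaction for fat mass to remove. The named contrast would then be close to zero before and after adjustment, even if fat explained the whole DS excess. The extent of explanation would have to come from a comparison chosen after the data are seen.

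**Working it through.** **What the documents supply.** 155 evaluable subjects with DS and 105 controls (section 6.2), and the Aim 1a and 1b models (sections 6.1.1 and 6.1.2). They give no fat levels, slopes or heights, so every effect size below is assumed. A two-sided 5% level is also assumed, since the plan states none.

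**The plan's own figure.** Aim 1b has no power statement. The primary-aim statement is for a between-group difference of 0.35 SD, which is a level and not an interaction. Power = Φ(0.35·√(e·155·105/260) − z). With Wilcoxon efficiency e = 0.955 this is 0.856 at one-sided 5% and 0.772 at two-sided 5%, against the stated value above 0.85. Nothing below depends on it.

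**Which coefficient carries what.** Let fat = a + b·Z + c·DS + d·DS·Z + error, with Z the centred BMI-Z, and risk = β·fat + γ·Z + τ·DS + error.

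- Without fat: DS coefficient = τ + βc; interaction = βd.
- With fat: DS coefficient = τ; interaction = 0.
- Change on adding fat: βc in the DS coefficient, βd in the interaction.

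The named contrast therefore shows only βd. A level excess due to fat, βc, shows only in the DS coefficient.

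**Size, constant excess.** Assume a fat index (fat for height) with c = 1.5, d = 0 and residual SD 1.2, β = 0.25, and residual SD of risk 1.

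- DS coefficient before fat: 0.25 × 1.5 = 0.375 SD.
- Residual SD before fat: √(1 + 0.25²·1.2²) = 1.044.
- SE: 1.044·√(1/155 + 1/105) = 1.044 × 0.1264 = 0.132.
- Detection: Φ(0.375/0.132 − 1.96) = 0.81.
- Interaction: 0.25 × 0 = 0, rejected at the nominal 5%.

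Simulation (2,000 data sets per cell) gave a DS coefficient of 0.372 to 0.377 (detected in 79 to 82%) and an interaction of −0.003 to 0.000 (rejected in 4.8 to 5.4%).

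A separate simulation (3,000 data sets; β = 0.35, fat slope 0.7 on BMI-Z, fat residual SD 0.6) shows both forms, with rejection rates in brackets:

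| Extra fat in DS | DS coefficient, without → with fat | Interaction, without → with fat |
|---|---|---|
| Constant (c = 1, d = 0) | 0.354 (78%) → 0.005 (5%) | −0.003 (5%) → −0.002 (5%) |
| Slope only (c = 0, d = 1) | 0.003 (6%) → 0.003 (6%) | 0.350 (77%) → 0.000 (5%) |
| Both (c = 1, d = 0.5) | 0.351 (77%) → 0.002 (5%) | 0.175 (28%) → 0.001 (6%) |

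**Size, excess rising with BMI-Z.** With the fat-index inputs, BMI-Z SD 1 and d = 0.5 or 1.0, the interaction before fat is 0.125 or 0.25. Its SE is about 0.132, so rejection is Φ(0.125/0.132 − 1.96) = 0.16 or Φ(0.25/0.132 − 1.96) = 0.47. Simulation gave 0.13 to 0.25, rejected in 15 to 45%. Here the named contrast is informative.

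**Precision of the added contrast.** Variance of the change ≈ β²·SE(c)² + c²·SE(β)². SE(c) = 1.2 × 0.1264 = 0.152; SE(β) = 1/(1.2·√255) = 0.052. The sum is 0.0014 + 0.0061 = 0.0076, so the SE is 0.087 and the 95% half-width about 0.17 SD. A bootstrap check (300 runs of 300 resamples, height in both models) gave 0.165 to 0.183 for height gaps of 0 to 15 cm, with the interval excluding zero in at least 99% of runs.

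**Why a BMI-Z value must be stated.** With an interaction in the model, the DS coefficient is the group difference at BMI-Z = 0 unless BMI-Z is centred. Section 6.1.1 expects half the DS group at or above the 85th percentile, which puts their median BMI-Z near Φ⁻¹(0.85) = 1.04.

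**Height.** Assume a within-group height SD of 8 cm. Adding height multiplies the variance of the DS coefficient by 1 + 0.241·(gap/8)², where 0.241 = 155·105/260². At 10 cm the factor is 1.38, the SE 0.155 and detection 0.68; at 15 cm they are 1.85, 0.179 and 0.55. Simulation gave 67% and 54%.

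The metric matters too, at gaps of 0, 5, 10 and 15 cm without height in the model. If fat for height drives risk, FM alone leaves a DS coefficient of 0.145, 0.229, 0.314 and 0.410, and FM/height² leaves 0.00. If kilograms of fat drive risk, FM alone leaves about 0.00, and FM/height² leaves 0.00, −0.13, −0.26 and −0.38.

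**The case against.** The strongest reply is that the plan answers its objective as written. The aim is to compare a relationship with BMI-Z between groups, so item b most naturally refers to the slope, and the interaction is a direct contrast for that. This stands: the named result is incomplete, not wrong.

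A second reply is that nothing is missing from the model. Section 6.1 has DS as the exposure and makes that comparison the basis for the sub-aims. If main effects are kept, as is usual, both DS coefficients exist once the models are fitted. This also stands, and it makes the gap one of reporting. A reader might infer that Aim 1b leaves the DS term out or cannot test mediation; the documents do not support that.

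Third, the hypothesis says worse at a given BMI-Z; it never says the excess is constant. A zero interaction in the constant-excess illustration is built in by assumption, and the interaction is informative if excess fat rises with BMI-Z. The point therefore applies to whatever part of the excess is shared across BMI-Z.

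Fourth, it would be tempting to say that the fat measure is undefined or that height is mishandled. The plain reading of FM in sections 2.1 and 6.1.2 is unindexed fat mass. The remark in section 5.1.7 that "this index increases with decreasing height, which is not ideal for children with DS" concerns left ventricular mass. No section proposes to bring height in only together with fat. What remains is that the Abstract notes short stature in DS, so one check on the metric is reasonable.

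**Conclusion.** The point holds as a gap in what Aim 1b commits to report. The named interaction contrast suits the slope reading and should stay. It cannot by itself give the extent to which fat explains worse risk at a given BMI-Z, because the part of that excess shared across BMI-Z appears in the DS coefficient.

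Under a purely constant, fat-driven excess of about 0.375 SD, the DS coefficient would be detected in about 80% of samples of this size, while the interaction would be rejected at about its 5% error rate. If the excess grows with BMI-Z, the interaction recovers some information, with rejection in roughly 15 to 45% of samples in the cases tried.

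The structural statement, which coefficient carries which part, follows from the model and needs no numbers. The magnitudes are illustrative only. They also leave out age, sex and pubertal stage, which the plan matches on or adjusts for. This is a cheap improvement to consider, not a flaw in the design.

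**What to change.** In section 6.1.2, keep the interaction and add the following for each risk factor:

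- Report the DS coefficient at a stated BMI-Z (for example the sample mean) without and with FM, fitted on the same subjects and with otherwise identical covariates.
- Report the change in that coefficient with a bootstrap confidence interval.
- If height is a covariate, include it in both models, so that a height effect is not credited to fat.
- Show one sensitivity analysis with fat scaled for height, for example FM/height². It should accompany FM, not replace it, since either metric can mislead depending on which form of fat drives risk.

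The cost is SAP wording and a little more analysis; stature and DXA fat are already measured. If height is used, the DS coefficient is less precise. Under the assumed inputs, with fat for height driving risk, detection of the DS excess before fat is added falls from about 80% to about 67% at a 10 cm height gap and 54% at 15 cm. Sample size, visits and procedures do not change.

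### Objective 1c asks how PWV and LV mass vary with BMI-Z, but the Aim 1c paragraph enters them only as added terms in the risk-factor models, and section 6.1 leaves open which model answers the objective

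*Combined protocol and SAP*

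**What the plan says.** Section 2.1, item c, sets the objective: "Assess cardiac end organ injury (pulse wave velocity (PWV) and left ventricular mass) in relationship to BMI-Z score in adolescents with DS and controls". The same item then turns to discrimination. That second half is analysed in section 6.1.3 ("With BMI-Z, and each risk factor taken individually, we shall estimate the c-statistic") and is not in question.

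The models in section 6.1 build on each other:

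- **Primary Aim paragraph:** a separate regression for each risk factor, with DS as the exposure and confounders added.
- **Aim 1a:** that model "will be modified to include an interaction term between DS and BMI-Z score for each CVD risk factor".
- **Aim 1b:** DXA fat mass joins the right-hand side ("Inclusion of FM in explaining CMR factors in the model").
- **Aim 1c:** starting again from the model already described, "we will add PWV as an indicator of end organ damage to assess additional information provided by PWV", with particular attention to how BMI-Z and risk-factor levels interact. Then: "This approach will be used for CPP and LV mass as well".

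The Primary Aim paragraph also says "Descriptive data analysis will summarize distributions of all risk factor measures" and includes CPP, PWV and LV mass in the list that follows. It ends by making the initial analyses the foundation for the sub-aims.

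**The concern.** The objective makes PWV and LV mass the quantities to be explained and BMI-Z the explanatory variable. The paragraph written to deliver it leaves the CVD risk factor as the response and adds PWV as one more explanatory term, just as Aim 1b adds fat mass. That answers a different question: what PWV tells us about the risk factor once DS and BMI-Z are known.

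An analyst who follows the Aim 1c paragraph will not produce the relation that the objective names. One who follows the Primary Aim paragraph and treats PWV as a risk factor will. The plan does not say which result answers objective 1c.

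There is also a conditional risk. If arterial stiffness lies downstream of the risk factor, the DS and BMI-Z coefficients in the PWV-adjusted model are not total effects and should not be reported as such.

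**Working it through.** The plan gives no figure for Aim 1c. The power statement in section 6.2 concerns a between-group mean difference, so there is nothing to reproduce for a slope. From the documents I use only the group sizes, 155 and 105. Everything else is an illustrative assumption: BMI-Z (Z) with SD 1, residual SDs of 1, and a risk-factor slope on BMI-Z of 0.25 in both groups.

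**1. What the Aim 1c model estimates.** Let R be the risk factor and P be PWV.

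- R = 0.25 Z + e
- P = s Z + ρ e + u, with s = 0.10 in controls and 0.30 in DS; ρ is the effect of the risk factor on PWV

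For the model as written, R ~ DS + Z + DS x Z + P:

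- coefficient of P: k = ρ / (1 + ρ²)
- coefficient of Z: 0.25 - k × 0.10
- coefficient of DS x Z: 0 - k × (0.30 - 0.10)

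| | ρ = 0 | ρ = 0.3 |
|---|---|---|
| P | 0 | 0.3/1.09 = 0.275 |
| Z | 0.25 | 0.25 - 0.0275 = 0.222 |
| DS x Z | 0 | -0.275 × 0.20 = -0.055 |

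None of these is 0.10, 0.30 or their difference of 0.20. Simulation at 155/105 agrees (0.248, -0.000, -0.001 for Z, DS x Z and P at ρ = 0; 0.222, -0.055, 0.275 at ρ = 0.3).

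**2. The opposite causal direction.** A second simulation let PWV drive the risk factor, with true PWV slopes (control/DS) of 0/0, 0.30/0.30, 0.20/0.60 and 0.60/-0.20. The as-written coefficients stayed at about 0.30 (BMI-Z), 0.15 (DS x BMI-Z) and 0.25 (PWV) in all four cases. The slopes that the objective asks about changed greatly and the model did not register it.

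**3. PWV as the response.** P ~ DS + Z + DS x Z gives 0.098/0.299 at ρ = 0 and 0.100/0.300 at ρ = 0.3. In the second set-up it recovers all four pairs to within 0.005.

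**4. Precision of the corrected analysis.**

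- SE of the slope difference = sqrt(1/155 + 1/105) / SD(BMI-Z) = 0.126 at SD 1. Simulated mean SEs are 0.128 (ρ = 0) and 0.134 (ρ = 0.3).
- Difference detectable with 80% power, two-sided 0.05: (1.96 + 0.84) × 0.126 = 0.35, or 0.36 with the simulated SE of 0.128. It is about 0.44 if BMI-Z SD is 0.8 and 0.30 if 1.2.
- Power for a difference of 0.20 at SD 1: about 0.35 analytically, 0.32 to 0.34 simulated.
- 95% half-width at SD 1: 1.96 × 0.126 = 0.25.
- With 20% of PWV or echo data unusable: SE 0.141, detectable difference about 0.40.

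**5. Size of the conditional risk.** Take a DS effect on the risk factor of 0.35 SD, ρ = 0.3 and a direct DS effect λ on PWV. The PWV-adjusted DS coefficient is 0.35 - k(0.35ρ + λ):

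- λ = 0: 0.35 - 0.275 × 0.105 = 0.321
- λ = 0.3: 0.35 - 0.275 × 0.405 = 0.239

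**The case against.** The best reply is that the outcome models are already planned. The Primary Aim paragraph names CPP, PWV and LV mass among its risk factor measures, in a run of physiological variables; it fits a model to each risk factor, compares each endpoint with weights, and calls these analyses the basis for the sub-aims. Apply Aim 1a's interaction to PWV and the required model results. Objective 1a's list, which ends "glucose tolerance, inflammatory markers, and adipokines)] in adolescents with DS and in matched controls", omits PWV and LV mass, but that proves little: CPP is in no objective and is still analysed.

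Much of this stands. A reader might infer that objective 1c has no analysis at all, and the documents do not support that.

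It does not settle the matter. The list is introduced as descriptive and also holds age, gender, race and BMI-Z itself, so it cannot be a list of responses as it stands. Adding PWV to a model whose response is PWV makes no sense, so the Aim 1c paragraph presupposes another response. Section 6.1.4, by contrast, states its outcome models for quality of life and body image outright.

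Three smaller points:

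- The objective speaks of a relationship and not of slopes. True, but slopes by group are its natural form given the interaction in Aim 1a.
- The control slope could be recovered by comparing models with and without PWV: (0.25 - 0.2225)/0.275 = 0.10. This is not planned, and it fails when the PWV coefficient is near zero.
- The Aim 1c text could be read as a PWV-outcome model that also contains the risk factor. With DS x BMI-Z kept, this recovers the difference of 0.20, but at ρ = 0.3 the slopes become 0.02/0.22 instead of 0.10/0.30.

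**Conclusion.** The concern holds as a conflict between two passages. The paragraph dedicated to Aim 1c describes a model that cannot give the relation of PWV or LV mass to BMI-Z; the Primary Aim paragraph can be read to supply one that does; the plan does not choose. The first statement is structural and does not depend on the assumed values, which only illustrate it.

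The reach is limited. The non-HDL-C, Aim 1a, Aim 1b and section 6.1.3 analyses are unaffected, and a reader should not infer that they are compromised. The total-effects caution applies only if PWV is downstream of the risk factor and someone reads the adjusted coefficients that way; the plan itself claims only additional information from PWV, and the unadjusted models remain. It is worth correcting because it concerns a stated part of the primary aim.

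**What to change.** State in the Aim 1c paragraph that PWV, CPP and LV mass are each fitted as the dependent variable on DS, BMI-Z, DS x BMI-Z and the planned confounders. Name the normalisation of LV mass chosen under section 5.1.7, for example DXA lean mass. Report the BMI-Z slope in each group and the slope difference with confidence intervals, and present the difference mainly as an estimate given its precision. Keep the PWV-adjusted risk-factor model as an additional analysis, with a note that its DS and BMI-Z coefficients are not to be read as total effects.

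The cost is one rewritten paragraph and a few more regressions on data already to be collected. The change makes the objective answerable but does not make the slope contrast well powered.

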## **6.2 Sample Size and Statistical Power**

Primary Aim: Assuming 155 evaluable children with DS and 105 evaluable children without DS for analysis and conservatively using nonparametric methods for comparison of CVD risk factors, power exceeds 0.85 to detect a between-group difference of 0.35 standard deviation (SD). For example, non-HDL-C is our primary CMR outcome measure, and 0.35 SD

---

corresponds to a difference of 7 mg/dl. A difference of 10 mg/dl is considered clinically relevant by pediatric cardiologists.

Secondary Aim: Power for the paired design can be assessed by assuming paired comparisons of residuals of a regression of BMI-Z on QOL and body image measures. Assuming that the outcomes, and thus residuals, will be continuous, power = 0.86 to detect as significant as little as 0.25 SD in differences between DS children and controls using nonparametric tests (Wilcoxon) that would be suitable for both continuous and ordered data. Thus, the sample should have substantial power to demonstrate even small differences between DS and matched controls.

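### Aim 1d states no correction for fitting and judging a combined screen in the same DS children; on the natural reading the AUC gain is overstated and its test is weak for small to moderate gains

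*Combined protocol and SAP*

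**What the plan says.** Section 6.1.3 sets out Aim 1d. On the analysis set: "This analysis will be confined to children with DS". Each risk factor is made binary, which requires "determination before analysis of a threshold of high versus low". For each screening measure, "we shall estimate the c-statistic, a measure of discrimination representing the area under the ROC curve". The last step goes from single measures to combinations: "we shall compare the additional discriminatory power of adding one screening measure to an existing screening measure, such as WC to BMI-Z". Its stated purpose is "to determine whether an additional screen is worth the expense and time".

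The method is given by citation: "These contrasts will be implemented using the methods outlined by" the authors of a cited textbook. Section 6.1.4 adds only that these methods are available in Stata.

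On numbers, section 6.2 begins "Assuming 155 evaluable children with DS and 105 evaluable children without DS for analysis", but its power statements concern comparisons of DS with controls. Section 6.1.1 says "we estimate 50% of subjects with DS will have BMI" at or above the 85th percentile, and only those children have an OGTT.

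The plan gives no combining model, test, optimism correction, validation sample, smallest worthwhile gain, or power or precision for Aim 1d.

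**The concern.** BMI-Z alone and BMI-Z plus waist circumference (WC) are nested. The combined score needs weights, and the plan mentions neither external weights nor a second DS sample, so the weights would come from the children in whom the score is then evaluated. Two problems follow if the gain is read off as a difference of two AUCs.

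- The fitted score is tuned to these children, so its AUC tends to rise even when the added measure carries no information.
- The usual variance for an AUC difference treats the fitted scores as fixed markers. With a useless added measure the two scores nearly coincide, the normal approximation fails, and the test loses its nominal size. The same defect costs power when the gain is real but small.

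At stake is the advice on whether clinicians should take a second measurement. It could rest on a gain that is too large as an estimate, next to a test that usually reports no significant added value even for a measure with a modest real benefit.

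**Working it through.** The plan gives no figure for Aim 1d, so there is none to reproduce. The check is by simulation.

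**Inputs from the plan.** Number of DS children: 155 (section 6.2). OGTT outcomes: 0.50 × 155 = 77.5, about 78 (section 6.1.1).

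**Assumptions, because the plan is silent.** Main settings: high-risk prevalence 20-30%, so 0.20 × 155 = 31 to 0.30 × 155 = 46.5 high-risk children; correlation of WC with BMI-Z 0.8-0.9; nominal level 5%. Wider settings: prevalence 10-50%, correlation 0.5-0.85, BMI-Z AUC 0.61-0.82, two-sided 5%, 1,500-2,000 replicates per setting.

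**Quantities computed.**
- Model A: logit P(high) = a0 + a1·BMI-Z. Model B: logit P(high) = b0 + b1·BMI-Z + b2·WC. Both are fitted to the same 155 children.
- Apparent gain: D = AUC(B) − AUC(A) in those children.
- AUC-difference test: D / SE(D), with the DeLong variance.
- Likelihood-ratio test: 2·(logL of B − logL of A), on 1 degree of freedom.
- Optimism: apparent gain minus the gain when the fitted models are scored in new children.

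**Useless added measure (b2 = 0).**
- Main settings: apparent gain +0.005 to +0.007, positive in about 73% of samples; in new children −0.005 to −0.008. Pairing the ends, optimism is 0.005 + 0.005 = 0.010 to 0.007 + 0.008 = 0.015.
- Same prevalence and correlation, with a dichotomised latent-normal outcome and BMI-Z AUC about 0.67: +0.007 to +0.010 against −0.008 to −0.010. Optimism is 0.007 + 0.008 = 0.015 to 0.010 + 0.010 = 0.020.
- Wider settings: +0.004 to +0.025 (largest at 10% prevalence with a weak BMI-Z), positive in 72-78%; in new children −0.004 to −0.016.
- Rejection at nominal 5%: AUC difference 0-0.3% (main) and 0-0.7% (wider); likelihood ratio about 5% (main) and 4.7-6.0% (wider).

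**Real gain, power with 155 children.**

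| True AUC gain | AUC difference, main | Likelihood ratio, main | AUC difference, wider | Likelihood ratio, wider |
|---|---|---|---|---|
| 0.012 | – | – | 2-3% | 25-32% |
| about 0.02 | 6-8% | 52-60% | 5-9% | 49-64% |
| about 0.03 | – | – | 9-27% | 58-92% |
| about 0.04 | 18-26% | 79-86% | 17-54% | 80-98% |
| 0.07-0.08 | 52-65% (at 0.08) | – | 39-68% | 93-99.5% |
| 0.114 | – | – | 85% | 99.9% |

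The latent-normal version gives 6-7% against 47-54% at a gain of 0.02, and 13-18% against 70-77% at 0.04.

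**Sample size.** At a true gain of about 0.021 (prevalence 25%, correlation 0.85), power of the AUC difference is 27% with 400 children, 69% with 800 and 90% with 1,200. About 1,000 would be needed for 80%.

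**Bootstrapping the raw AUC difference** (250 replicates, score held fixed or refitted). With no true gain it rejects in 0%, or 2.4% for the refitted percentile interval. Wald power is 3-4% at a gain of about 0.02 and 16-18% at about 0.04. Percentile-interval power is 7-26% and 22-51%; the upper figures are for refitting.

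**The case against.** The strongest reply is that the plan never says it will take an uncorrected difference of two AUCs. It names the c-statistic for single measures and leaves the added-value step to a textbook that cannot be consulted here. That stands, and it makes the finding conditional. The inference is still the natural one: the sentence on added discriminatory power directly follows the definition of discrimination as area under the ROC curve, and nothing in the plan offers an alternative. If another method is intended, the text needs to name it.

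A reader might infer that Aim 1d would declare useless screens worthwhile. The documents and the numbers do not support that. The false gain is in the point estimate; the test almost never declares one, and the plan nowhere treats any positive AUC change as success.

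A reader might also infer that the analysis has almost no power for any real gain. That holds only up to about 0.02. Power is low to moderate near 0.04, 52-65% at about 0.08 and 85% at 0.114.

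Two further points stand. A significant likelihood-ratio test shows that WC carries information beyond BMI-Z, not that measuring it is worth the cost: at a gain of only 0.012 it already rejects in 25-32% of samples. And the reach is limited. The objective in section 2.1 asks whether BMI-Z or other measures discriminate better, and such head-to-head comparisons need no fitted weights. Only the add-on step of one sub-aim is affected.

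**Conclusion.** The point holds in conditional form. If added value is judged by contrasting c-statistics in the same DS children without correction, the estimated gain for a useless measure is too high by roughly 0.01 to 0.02 relative to new children. The accompanying test is very conservative and weak for gains of about 0.02 to 0.04, the range in which a likelihood-ratio test has roughly 50% to 86% power at the main settings.

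Only the 155 children, and about 78 for OGTT outcomes, come from the plan. Prevalence, correlation, BMI-Z AUC and the 5% level are assumptions. The direction was the same in every setting tried; the size was not, and it grows when high-risk children are few. OGTT outcomes were not simulated separately, but with half the children they should fare worse.

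This is more than missing detail, because a better method is available at little cost. It should be changed, but it does not touch the primary outcome.

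**What to change.** In section 6.1.3, state that for each risk factor a logistic model with BMI-Z alone and one with BMI-Z plus the added measure will be fitted in the DS children, and then:

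- test the added term by likelihood ratio;
- report the AUC gain after bootstrap optimism correction, refitting both models in every resample, with a confidence interval and a statement of how the interval is formed;
- base the judgement on a second screen on the corrected gain and its interval, not on the p-value alone. Stating beforehand the smallest gain that would count as worthwhile would make that judgement checkable;
- keep ROC contrasts for head-to-head comparison of single measures.

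The cost is some SAP wording and a short bootstrap in Stata or R, both already listed in section 6.1.4. No new data or procedures are needed. The downside is slightly smaller reported AUC gains and a little more analysis work.
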